2.2. Relevant preliminary data:¹

This application is the next phase of a previously approved application (IRB ID: STUDY00000413)

2.3. Scientific or scholarly background:

A pilot randomized controlled trial (RCT) (n=251) of the PARENT intervention in 2 clinics demonstrated robust improvements in parent- reported receipt of WCC services (e.g., psychosocial screening, health education and guidance, and developmental screening, surveillance), experiences of care, and reduced emergency department (ED) visit.

2.4. Prior approvals:

None

3. Study Endpoints²

3.1. Primary and secondary endpoints:

Improvement of WCC services (e.g., psychosocial screening, health education and guidance, and developmental screening, surveillance).

Improvement of parent experiences of care

Reduction in emergency department (ED) visits

3.2. Primary or secondary safety endpoints:

This study has minimal risk to participants. There are no safety endpoints.

4. Drugs, Devices and Biologics³

4.1. Manufacturer and name of all drugs, devices and biologics:

N/A

4.2. Description and purpose of all drugs, devices and biologics:

N/A

4.3. Regulatory status of all drugs, devices and biologics:⁴

N/A

4.3.1. Drugs or Biologics:

IND Exempt. Explain:⁵ [Click here to enter text.](#)

IND.

4.3.2. Devices:

IDE Exempt. Explain:⁶ [Click here to enter text.](#)

Abbreviated IDE / Non-Significant Risk. Explain:⁷ [Click here to enter text.](#)

IDE / Significant Risk.

4.4. Plans to store, handle, and administer any study drugs, devices and biologics so they will be used only on subjects and be used only by authorized investigators:

N/A

5. Procedures Involved

5.1. Study design:⁸

Our community partners are two federally-qualified health centers (FQHC). FQHC #1 is located in the Tacoma area in Washington and the FQHC #2 is located in the San Fernando/Santa Clarita areas in Los Angeles, CA. FQHC #1 has 4 clinics participating in the study and FQHC #2 has 6 clinics participating in the study. The total number of clinics participating in the study is 10. The cluster randomization was conducted at the end of 2017 by the study statistician. The clinics were placed in blocks by FQHC, location and size and the assignment to control or intervention was done using a computer-generated random allocation. Below are the cluster-randomized assignments, stratified by block and clinic size:

Block	FQHC #1	Assignment
1	Eastside Lakewood	Intervention Control
2	Parkland Spanaway	Control Intervention

Block	FQHC #2	Assignment
1	Canoga Park Van Nuys	Control Intervention
2	Pacoima San Fernando	Intervention Control
3	Santa Clarita Valencia	Intervention Control

The five clinics randomized to intervention will implement the newly adapted model of well child check-up visits for children ages 0-3. The five clinics randomized to control will continue to use the same services that the clinics provide--their usual check-up visit as their typical clinician-led visit (well-visit time slots vary by practice).

Parent/legal guardians will receive the same services offered by these clinics for their child's health care whether they participate in this study or not.

Components of the newly designed model of WCC:

The PARENT intervention was adapted during the Project Working Group meetings in partnership with the two FQHCs (Phase 1: IRB ID: STUDY00000413).

- **Parent Coach at each visit.** The Parent Coach is a Spanish/English-bilingual trained health educator hired by the respective FQHC who received seven weeks of training. The training consisted of self-directed learning based on *Bright Futures Guidelines, Third Edition*, relationship building with community organizations near each clinical site; mock visits; and pediatrician-observed visits with feedback at the practices. The Parent Coach will be available at the intervention clinics to serve as the primary provider of anticipatory guidance, psychosocial screening and referral, and developmental/behavioral guidance and screening at each check-up visit. They will talk to parents about any concerns parents might have about feeding, sleeping, parenting, safety, or other issues. The parent coach will use an adapted version of the *Bright Futures Previsit Questionnaire, Third Edition* for each well-child care visit to guide the visits with the parent. They will document their visit in the child's Electronic Health Record.
- **Well Child Help Line.** The Parent Coach will be available to answer parents' preventive care-related questions, conduct parent follow-up calls and visit reminders during business hours.
- **HealthyText Messages.** Parents will be offered the text messaging service at study enrollment and research staff will process the enrollment by providing the parent's cell phone #, child's DOB and language preference (English/Spanish). The library of text messages (English and Spanish) were adapted from Healthy-TXT, a text messaging service (Healthy-TXT, LLC, Chicago, IL), to the needs of the FQHCs. If parent choose to sign up, they will receive text messages each week focused on age-appropriate anticipatory guidance, health education, and reminders for WCC visits. Most messages include a link to an educational website (e.g., healthychildren.org) with a video or written information on that specific topic, or the message may include the clinic's telephone number for visit scheduling, the parent coach number or other information (e.g., poison control hotline). At any time, parents will be able to text STOP to end the service.

5.2. Research procedures:⁹

Intervention and Control clinics: Parents/legal guardians checking in for a WCC visit or a visit in between for an infant ≤12 months will be approached by research staff. Research staff will obtain a schedule of WCC visit prior to visiting the clinic. The schedule will include date, type of WCC visit, language, MRN, and child's age in weeks or months, parent name, parent phone number, and home address.

Parent/ legal guardians will be approached while waiting for their WCC visit or by phone if research staff are unable to approach in-person.

Clinic flyer procedure:

Clinics will have flyers on display about the study as a method for alerting parents to the possibility of being approached by research staff. Parents may take a flyer from the clinic to initiate communication with study staff to determine eligibility, learn more about the study, review the information sheet, and give verbal consent.

Clinic recruitment procedure:

Research staff will let the clinic staff and front desk staff know when arriving and verify the schedule. The front desk staff will let parents/legal guardians know that someone is at the clinic to talk to them about the research study. If parent/legal guardian agrees to be approached, the front desk staff will let the research staff know.

Research staff will explain the study, screen for eligibility (they will be asked some questions), provide the parental permission and consent form, and obtain consent. When possible, parents/legal guardians will be given the opportunity to discuss the study in a private room.

Research staff will conduct the baseline survey after screening and obtaining consent while parent/legal guardian is waiting for their WCC visit in the waiting area. We will assign IDs to all screened parents/legal guardians but will conduct the survey only with those wanting to participate and if they are eligible. If the survey is not completed during the waiting room time period, we will ask parent/legal guardian if it is possible to complete the survey at the end of their WCC visit or by phone the same day or any other day but not later than 14 days from date of enrollment.

Phone call recruitment procedure:

When research staff are limited from recruitment on-site, clinic sites will be informed of pre-screened visits that are anticipated to be eligible for enrollment.

CHC and NEVHC sites:

1. Clinic Staff approach in-person: When clinic staff are available in-person to communicate with the parent/legal guardian of a pre-screened patient (pre-screened by the research team), the clinic staff will give a physical copy of the information sheet, and will ask if the research team can call the parent/legal guardian to explain the study, screen for eligibility, review the information sheet, and obtain verbal consent. Parents/legal guardians will have the option to decline a call from the research team by letting clinic staff know they do not want to be

contacted. Clinic staff will communicate with the research team to let them know which families were approached by clinic staff and agreed or declined to receive a call from the research team.

2. Clinic staff approach over the phone: When clinic staff conduct pre-visit calls by phone to review appointment procedures with a parent/legal guardian, the clinic staff will communicate with the parent/legal guardian of a pre-screened patient (pre-screened by the research team) to inform them of the study. The clinic staff will ask if the research team can call the parent/legal guardian to explain the study, send the parent an information sheet, screen for eligibility, review the information sheet, and obtain verbal consent. Parent/legal guardians will have the option to decline a call from the research team by letting clinic staff know they do not want to be contacted. Clinic staff will communicate with the research team to let them know which families were approached by clinic staff and agreed or declined to receive a call from the research team.

Additional recruitment method for CHC patients:

1. Parent/legal guardians of a pre-screened patient (pre-screened by the research team) will be mailed an (i) opt-out letter co-signed by CHC's medical director and Study PI and an (ii) information sheet. Parent/legal guardians will have the option to decline a call from research staff by responding to the letter by email, call, or text. Research staff will call to explain the study, screen for eligibility, review the information sheet, and obtain verbal consent.

Additional recruitment procedure details:

For those approached by phone, study staff who have access to the clinic WCC visit schedule and that have received training to use the clinic's EHR will document the consent process by entering the date and time in RedCap.

We will collect information on the number of people approached, the number of people who agreed to participate and the number of people who refused to participate and the reasons for their refusal.

We will collect contact information from the enrolled parent/legal guardian and spouse/partner (home and cell phone, email) to telephone them to complete the baseline survey, if needed. The information will be verified at each subsequent contact for the follow up surveys at 6-month and 12-months from date of enrollment. We will also ask parents to provide contact information for three relatives/friends who will always know their whereabouts. Because this study population frequently changes phone numbers, we will also ask participants to provide any social media handles, if they are willing, so that the study team can direct message them. Direct messaging will be utilized to get updated phone numbers or schedule a phone conversation and no other purposes. Additionally, to support retention we will contact participants by cell phone and email at 3- and 9-month time points to remind them of their study participation as well as confirm their contact information has not changed. Furthermore, we will send participating families a card for their baby's first birthday and for New Years from the research team to encourage engagement, remind them of their participation, and support follow-up survey retention.

The research staff will ask parents/legal guardians questions about their experiences in getting care so that we can compare the two types of well-child care.

We will conduct three waves of survey data (baseline, 6-month and 12-month) collection and chart review at the end:

- Baseline Survey (at enrollment): Experienced research staff will be responsible for data collection. Upon enrollment, parents will participate in a 35-minute survey to collect baseline demographic data on the infant, parent, and household and child's medical history.

- 6-Month Survey (participant retention survey by phone): Research staff will conduct a 15-minute phone survey at 6-months post-enrollment to aid in participant retention. The 6-month survey will update the child's medical history, household changes, and healthcare utilization (e.g., ED utilization).
- 12-month Survey: At 12-months post-enrollment, all participants will be asked to complete a 40-minute survey by phone. This survey administration will include the Promoting Healthy Development Survey (PHDS-PLUS), a parent survey that assesses the provision of nationally recommended WCC services. We will use the PHDS-PLUS to determine parent perceived receipt of recommended WCC services, appropriate follow-up, and health care utilization. Additional questions on social determinants screening and referral are included and drawn from the PHDS-PLUS as well as the National Survey of Early Childhood Health. We will also use items on overall satisfaction of care from the Consumer Assessment of Healthcare Providers and Systems (CAHPS) Health Plan Survey and family-centeredness of care from the National Survey of Children's Health. Using previously validated parent survey tools, we will collect data on our exploratory measures of parental mental health, perceived parenting self-efficacy and parenting behaviors.
For the 6-month and 12 month follow up surveys, we will contact study participants two weeks before the due date. If we are unable to reach them by the due date, we will continue calling them up to three months after the due date to complete the survey.
- Chart review: After completing the three waves of survey data collection, we will conduct chart review. The chart review includes clinic visits, ED visits, services received at those visits, immunizations, and status of referrals.

5.3. Data sources that will be used to collect data about subjects:¹⁰

Parent-report surveys and chart review from electronic medical records. All surveys, scripts, and data collection forms are attached in the Supporting Documents page

5.4. Data to be collected, including long-term follow-up data:¹¹

Baseline Survey (at enrollment), 6-Month Survey (participant retention survey) and 12-month Survey and Chart review at 12-month post enrollment.

6. Data and Specimen Banking¹²

6.1. Complete list of the data and/or specimens to be included in the bank:¹³

Names and contact information for participants enrolled prior to March 2020. Participant baseline data prior to March 2020.

6.2. Location of data and/or specimen storage:¹⁴

RedCap and WCC Redesign study shared drive

6.3. List of those with direct access to data and/or specimens in the bank:

Study staff who are both on the WCC Redesign project and the COVID Survey Study (STUDY00002666, approved by the SCH IRB on 07/01/20).

6.4. Length of time data and/or specimens will be stored in the bank:

Data will not be stored in a separate bank but will be accessed only by the COVID Survey Study for the length of that study.

6.5. Procedures for protecting the confidentiality and privacy of the subjects from whom the data and/or specimens were collected:¹⁵

Only study team members who currently have access to the information as part of the WCC Redesign study will access information for the purposes of COVID Survey Study recruitment. Contact information will be accessed, per the appropriate waivers (approved for the COVID Survey Study). Only WCC Redesign data from those who consent for enrollment in STUDY00002666 will be accessed.

6.6. How the data and/or specimens will be made available for future use:

Only relevant research staff will have access to the data.

6.6.1. Who can request data and/or specimens from the bank:

Only the COVID Survey study will be accessing this data.

6.6.2. Format in which data and/or specimens will be provided:

The COVID Survey Study staff will have full access to the RedCap data and participant contact information as it is stored in the study shared drive. The same staff works on both projects.

6.6.3. Process for investigators to request data and/or specimens:¹⁶

Use of the data from the WCC Redesign Study is limited to the COVID Survey Study and the same study staff are on the two studies, so no process to request data has been established.

6.6.4. Restrictions on future use:¹⁷

No other studies are being given access to this study data at this time.

6.6.5. Plan for providing data results from banked data/specimens:

Any plan to share results would be covered within the COVID Survey Study protocol.

7. Sharing of Results

7.1. Plan to share results with subjects/others:¹⁸

The results of the evaluation will be shared with participants using a flyer. The results will be presented only in aggregate form and with data that is de-identified. We will not put any data in the child's medical record

8. Study Timelines

8.1. Duration of an individual subject's participation in the study:

12 months

8.2. Duration anticipated to enroll all study subjects:

12 months

8.3. Estimated date for the investigators to complete this study:

June 2021

9. Study Population¹⁹

9.1. Inclusion criteria for each subject population (e.g., patients, parents, providers):

Parent/legal guardian-Child dyad attending well child check-up visits or visits in between for a newborn to 12-month.

Parent is English or Spanish proficient

For multiple gestations, one infant will be randomly selected as the index child. Infants with special health care needs will not be excluded from the study, since these children generally need the same recommended preventive care services.

9.2. Exclusion criteria for each subject population:

More than one child attending WCC

Legal guardian of child is under 18 years of age

Parents who are employed by the CHC/NEVHC

Either member of the dyad previously enrolled

Sick-visit

Parents/legal guardian planning not to continue receiving well child care services at this clinic for their child in the next 12 months

9.3. Vulnerable populations involved in the study:²⁰

Children/Teenagers²¹

Risk assessment specific to this vulnerable population and additional safeguards:²²

This study does not involve direct interaction with children but involve minimal interactions with the parents/legal guardians of the children attending well-child care visits to complete the study surveys. The minimal risk status of this study does not indicate the need for additional safeguards for these populations.

Children who are Wards of the State²³

Risk assessment specific to this vulnerable population and additional safeguards:

[Click here to enter text.](#)

Adults Unable to Consent²⁴

Risk assessment specific to this vulnerable population and additional safeguards:

[Click here to enter text.](#)

Neonates of Uncertain Viability or Non-Viable Neonates²⁵

Risk assessment specific to this vulnerable population and additional safeguards:

[Click here to enter text.](#)

Pregnant Women²⁶

Additional safeguards:

This study involves minimal interactions with pregnant women who might be the parents/legal guardians of the children attending well-child care visits to complete the study surveys. The minimal risk status of this study does not indicate the need for additional safeguards for these populations.

Prisoners²⁷

Additional safeguards:

[Click here to enter text.](#)

Economically or educationally disadvantaged persons²⁸

Additional safeguards:

This study involves direct interaction with economically or educationally disadvantaged persons and the following safeguards aid to minimize coercion or undue influence. (1) The recruitment process at the control and intervention sites have been designed to ensure participation is voluntary. (2) Recruitment materials do not promise "free" services or treatment, nor do they emphasize direct benefit to the participating subject during the research. (3) Incentive for research participation are commensurate with the risk, discomfort, and inconvenience involved in research, and financial or gains are not overly compelling. (4) Consent documents are written in language that is understandable to participants. (5) Study materials have been designed for the possibility of limited reading skills and the need to communicate in a foreign language (e.g., Spanish). (6) Participant will be reminded of their rights as a participant to ensure open and free communication between researcher and the prospective subject. The minimal risk status of this study does not indicate the need for additional safeguards for these populations.

10. Number of Subjects

10.1. Total number of subjects to be enrolled locally:²⁹

100 parent/legal guardian-child dyads per each of the four clinics in Tacoma, WA. For a total of 400.

10.2. Total number of subjects to be enrolled across all participating sites:³⁰

100 parent/legal guardian-child dyads per each of the 10 clinics. For a total of 1,000.

10.3. Number of screened subjects versus the actual number enrolled in the research:³¹

2 to 1. In other words, we will expect to screen doubled the number of actual people enrolled in the study

10.4. Power analysis:

The power calculation is based on WCC quality (anticipatory guidance) and ED visits (2 or more), with a 1:1 randomization of 10 sites into the intervention and control groups. We use the mean and standard deviation (SD) of anticipatory guidance and the rates of 2 or more ED visits as observed in our pilot RCT. For anticipatory guidance, we use the larger SD from the two groups to have a conservative power estimation for this variable. The calculation assumes an intra-class correlation of 0.01 based on previous delivery systems design cluster RCTs among similar populations^{81, 82} and the fact that the data analysis will be adjusted for important baseline covariates when comparing the intervention versus control groups⁸³. A 20% dropout rate is assumed at the patient level. Two-sided tests are used with a type I error rate of 0.05. With an N of 75 per site, we will have at least 80% power to detect the intervention effect for both anticipatory guidance and ED visits. After accommodating a 20% dropout rate at the patient level, the N per site is 94, or a total sample of 940 participants.

11. Withdrawal of Subjects

11.1. Anticipated circumstances under which subjects will be withdrawn from the research without their consent:

Subjects can choose whether to be in this study or not. If they agree to participate, they may withdraw their consent at any time without impacting their care. For this study, we do not anticipate the need to withdraw subject due to investigator judgement.

11.2. Procedures for orderly termination:

N/A

11.3. Procedures that will be followed when subjects withdraw from the research, including partial withdrawal from procedures with continued data collection and withdrawal from data/specimen banking:

Data collected on any withdrawn subjects will be removed from the analysis

12. Risks to Subjects**12.1. Reasonably foreseeable risks to subjects (include each study population, each arm, and optional procedures):**

There is a risk that confidentiality or privacy could be breached and people could find out if someone was in the study.

12.2. Procedures with unforeseeable risks:

N/A

12.3. Procedures with risks to an embryo or fetus should the subject be or become pregnant:

N/A

12.4. Risks to others who are not subjects:

N/A

12.5. Procedures performed to lessen the probability or magnitude of risks:

N/A

13. Potential Benefits to Subjects**13.1. Potential benefits that individual subjects may experience from taking part in the research.³²**

We do not anticipate any direct benefit to participating subjects.

14. Data Analysis/Management**14.1. Data analysis plan, including statistical procedures:**

We will compile descriptive statistics on all outcome variables, composite scores, and covariates. We will report means, medians, and standard deviations for continuous variables, create graphical displays to visualize distributions, and transform variables with non-normal distributions. Next, we will use multivariable analyses to examine differences between the control and intervention groups on the measures described above. From these analyses, we will estimate intervention effects. An intent-to-treat approach will be used, that is, parents will be analyzed according to the assigned group regardless of deviations from the study protocol. Sensitivity analysis will be conducted by performing the analyses with and without outliers and influential data points. Missing values will be excluded from the analysis if the missing rate is low (< 10%). If the missing rate is more than 10%, data may also be imputed using multiple imputation techniques and the analysis can then be done based on the complete, imputed datasets. All tests are two-sided, and p values < 0.05 are considered statistically significant.

Specific Aim 1: We will analyze anticipatory guidance based on data collected at 12-months post enrollment. We will assess intervention effect on anticipatory guidance via linear mixed effects models that involve random effects to capture data clustering within clinic, given

the fact that randomization is done at the clinic level. The outcome may be subject to transformation prior to fitting the model if non-normality is observed. The analysis will include intervention status as the main independent variable, adjusted for baseline covariates and other confounding factors. We will also test possible interaction effects between intervention and these covariates. All other outcome variables to measure experiences of care and receipt of other nationally-recommended WCC services are regarded as secondary. Each outcome will be analyzed using linear or generalized linear mixed effects models depending upon data distributions, with a similar setting as described above for anticipatory guidance.

Specific Aim 2a: Intervention effects on healthcare utilization (ER visits, hospitalizations, urgent care visits, regional center/early intervention, maternal mental health, support groups (e.g., breastfeeding, parenting classes), dentist, case management/social services) will be assessed using generalized linear mixed effects models for binary or count data with a similar setup as outlined for Aim 1. The model will include random effects to capture data clustering within clinic and the primary independent variable is intervention status. The analysis will be adjusted for any baseline child, parent, or household characteristics that are significantly different between control and intervention groups. We will also test interaction effects between intervention and the covariates.

Specific Aim 2b: Cost/cost-offset Analysis. We will conduct our analysis from the perspectives of the “social planner”⁸⁰ and of the payer (e.g., health plan or medical group), and consider intervention costs (direct and indirect) and cost offsets.

Specific Aim 4: We will utilize the same approach as described for Specific Aims 1 and 2a; i.e., linear or generalized linear mixed effects models, depending on the distribution of the outcome variables.

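### Section 11.3 removes all data on withdrawn families, a post-allocation exclusion that departs from the intent-to-treat principle in 14.1; the likely bias is small and the repair is cheap

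*Combined protocol and SAP*

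**What the plan says.** The heading of 11.3 asks for the procedure on withdrawal, "including partial withdrawal from procedures with continued data collection". The whole answer is: "Data collected on any withdrawn subjects will be removed from the analysis". It does not distinguish by timing, by type of withdrawal, or by what the family wishes for data already given. No other section keeps a withdrawn family's data.

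Section 11.1 describes withdrawal as a matter of consent: families are told that "they may withdraw their consent at any time without impacting their care". Section 20.4 adds that they are asked at the 6- and 12-month contacts whether to continue.

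On analysis, 14.1 says: "An intent-to-treat approach will be used, that is, parents will be analyzed according to the assigned group regardless of deviations from the study protocol". Missing values are excluded when the missing rate is below 10%; above that, "If the missing rate is more than 10%, data may also be imputed using multiple imputation techniques". Under Aim 2a, ED use and other utilization "will be assessed using generalized linear mixed effects models for binary or count data with a similar setup as outlined for Aim 1". No ED data source or time window is named there.

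On data, section 5.2 describes a baseline survey, a 6-month phone survey that includes ED use, a 12-month survey, and a chart review after all three waves that includes ED visits. Section 10.4 names 2 or more ED visits as one of the two outcomes behind the power calculation.

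**The concern.** Section 5.1 puts the clinic randomization at the end of 2017, before families were enrolled. Every family withdrawal therefore happens after allocation, and removing withdrawn families makes the analysed groups depend on something that follows allocation. Intent-to-treat exists to avoid that.

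Three kinds of information are at stake:

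- baseline data, for any family that completed the baseline survey;
- the 6-month ED report, for a family that leaves after that survey (one with 2 or more visits by then has already met the ED outcome used for power);
- chart-review ED data, for a family that stops surveys but would still permit chart review. The blanket rule has no category for such a family.

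If withdrawal is related to both arm and ED use, the ED comparison can be biased. The removed records are also those that multiple imputation under 14.1 would draw on.

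**Working it through.** **The plan's own figure.** Section 10.4: 75 / (1 − 0.20) = 93.75, rounded up to 94 per site, and 94 × 10 = 940. This reproduces. If every planned dropout were a formal withdrawal (an upper bound), 100 × 0.80 = 80 per site would remain, or 94 × 0.80 = 75.2. Either meets the 75 required.

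**Assumed inputs.** The documents give no ED rate, no formal-withdrawal rate and no recall window. Assume:

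- no true effect, with 20% of families in each arm having 2 or more ED visits in 12 months;
- a negative binomial yearly count, split evenly over two half-years that share a gamma frailty of variance 1, which gives a mean of 0.809 a year;
- a 6-month survey that covers ED use since enrolment;
- intervention families who withdraw do so after the 6-month survey, and are twice as likely to withdraw after any ED visit in the first half-year;
- control withdrawal unrelated to ED use.

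**Rate among withdrawn families.** The half-year mean is 0.4045.

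- P(no visit in first half) = 1/1.4045 = 0.712, so P(any visit) = 0.288.
- P(2 or more in the year | none in first half) = (0.288/1.288)² = 0.050.
- P(2 or more in the year | any in first half) = (0.20 − 0.712 × 0.050)/0.288 = 0.571.
- Among withdrawn families: (0.712 × 0.050 + 2 × 0.288 × 0.571)/(0.712 + 2 × 0.288) = 0.283.

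**Rate after exclusion.** With withdrawal proportion W, the rate left is (0.20 − W × 0.283)/(1 − W). The odds ratio (OR) compares its odds with 0.25, the odds at 20%. The standard error uses 375 per arm (5 × 75) and design effect 1 + 74 × 0.01 = 1.74: SE of log OR = √(2 × 1.74/(375 × 0.2 × 0.8)) = 0.241. The false-positive rate is P(|Z + shift| > 1.96), a normal approximation.

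| Intervention withdrawal | Rate left | OR | Shift in SE | False-positive rate |
|---|---|---|---|---|
| 2% | 19.8% | 0.99 | 0.04 | 5.0% |
| 5% | 19.6% | 0.97 | 0.11 | 5.1% |
| 10% | 19.1% | 0.94 | 0.24 | 5.7% |
| 10%, withdrawal ratio 3, frailty variance 2 | 18.3% | 0.90 | 0.45 | 7.4% |

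With a withdrawal ratio of 1 (unrelated to outcome), the OR is 1.00.

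**How kept data are used also matters.** Take 10% withdrawal unrelated to outcome, where exclusion is unbiased. Suppose withdrawn families are counted only when already known to have 2 or more visits. P(2 or more in first half) = 0.288² = 0.083, and the rate becomes (0.9 × 0.20 + 0.1 × 0.083)/(0.9 + 0.1 × 0.083) = 20.7%, OR 1.05. Keeping the data and using them this way creates a bias that exclusion does not have.

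Imputing from families with the same 6-month ED use returns 20.0% when withdrawal depends on that use; this follows by construction. If withdrawal instead depends on ED use after month 6, imputation gives 19.3% (OR 0.96) against 19.1% (OR 0.94) with exclusion, a slight gain.

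**The 10% rule.** With total loss L and formal withdrawal w, the missing rate computed after removal is (L − w)/(1 − w). It falls below 0.10 when w > (L − 0.10)/0.90. At the planned L = 0.20 this needs w > 0.111, which is 0.111/0.20, or about 56%, of all loss.

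**The case against.** The strongest defence is that 11.3 may honour a promise. Section 11.1 speaks of withdrawing consent, and the consent pages are not in the copy reviewed. If families were told their data would be removed, the rule is proper for them. That stands, and the fix must allow for it.

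Several stronger readings are tempting, and the documents do not support them:

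- *That 11.3 flatly contradicts 14.1.* The intent-to-treat sentence speaks of protocol deviations, and withdrawing consent is not obviously one. The conflict is with the principle.
- *That every withdrawal destroys ED data.* A 6-month ED report exists only for families who leave after that survey, and a family that stops when asked at that contact may never give one. If Aim 2a uses only the 12-month survey or chart data, an early withdrawal may lose no analysed ED outcome. The exclusion in the table would then occur anyway unless imputation or chart review filled the gap.
- *That the anticipatory-guidance result is affected.* It uses 12-month data, which a family that left earlier never gave. Only withdrawal after the 12-month survey would delete a score.
- *That the 10% imputation threshold is being evaded.* Section 14.1 does not define the denominator, but formal withdrawals would have to exceed 11.1% of families, imputation above 10% is optional anyway, and section 5.2 points more to lost contact than to formal withdrawal.

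It is also fair to say that the calculation imposes outcome-related withdrawal on one arm. The same pattern in both arms under no effect gives an OR of 1.00.

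**Conclusion.** The point holds as a minor one. Section 11.3 states, rather than leaves open, an exclusion after allocation that the intent-to-treat principle would avoid. It also leaves unanswered the heading's question about partial withdrawal.

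A reader might infer that the ED comparison will be biased. The documents do not show this: they give no formal-withdrawal rate and no evidence that withdrawal differs by arm or depends on ED use, and they do not say whether families lost to follow-up count as withdrawn. Under the assumed one-arm pattern, the shift is 0.11 SE at 5% withdrawal and 0.24 SE at 10%, and at most 0.45 SE over withdrawal ratios of 1 to 3, frailty variances of 0.5 to 2 and withdrawal up to 10%. The planned sample size is not threatened. The case for change rests on low cost and avoidable loss of data.

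**What to change.** Replace the sentence in 11.3 with: 'Data collected up to withdrawal are kept and analysed in the assigned arm, where consent permits; data are removed only if the participant revokes permission to use them. Stopping surveys is recorded separately from refusing chart review, and chart review is used for ED visits where still permitted. Withdrawn families count in the missing rate in 14.1, and withdrawals are reported by arm and clinic.'

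Add to 14.1: 'Where imputation is used, baseline data and 6-month ED use enter the imputation model. Partial-year ED data are not used by counting only withdrawn families already known to have 2 or more visits.'

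The cost is one paragraph in 11.3, two sentences in 14.1, one tracking field and some imputation programming, with no extra families. The downside is that consent or information-sheet wording may need alignment through the IRB. Families promised removal stay under those terms, so the new rule would change nothing for them. Imputation also assumes that withdrawal depends on recorded data, so it reduces the possible bias but does not guarantee its removal.
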